5.5.2 TMZ

TMZ-related toxicities should be managed as per local practice. Dose modifications for TMZ are allowed and should follow the standard of care at the institution except as instructed in sections 5.5.3.2, 5.5.3.3 and 5.5.3.4 below. In case of any AEs leading to TMZ interruption or delays not considered related to TG02, TG02 should continue as scheduled if medical condition allows it. If TMZ is interrupted due to toxicity, upon its resolution, TMZ should be restarted only at the next cycle.

During dose escalation, an interruption of TMZ for >25% of the planned total dose in Cycle 1 will be considered a DLT (see section 5.2.1).

5.5.3 TG02

5.5.3.1 For all groups

The following dose levels of TG02 will/can be used:

- 150 mg (groups A,B,C)
- 100 mg (groups A,B, C)

TG02 dose should not be reduced below 100 mg. If a patient's initial or current dose is 100 mg and the patient experiences a toxicity requiring TG02 dose reduction as described in the tables below, the patient should be discontinued from study treatment.

TG02 should not be skipped for more than 28 days. If TG02 cannot be re-introduced within 28 days, the patient should be discontinued from the study treatment.

In case of uncertainty regarding dose modifications described in the tables below, please contact the Sponsor.

In all cases, appropriate symptomatic treatment should be considered to manage the AE.

5.5.3.2 Group A

5.5.3.2.1 Dose escalation phase

Cycle 1: no TG02 dose reductions are allowed in Cycle 1, except if a patient experiences a DLT.

Skipped doses for TG02 are allowed. A “skipped dose” for TG02 when RT is not interrupted means that one or more single doses will be omitted and not replaced, in order not to change the temporal relationship with RT.

For example, if TG02 is planned on days 1, 4, 8 but day 4 has to be omitted, TG02 can be restarted on day 8 if the AE is sufficiently resolved: TG02 is always restarted on a scheduled dose day. Skipping TG02 for >25% of the planned total dose in Cycle 1 will be considered a DLT (see section 5.2.1).

Toxicities possibly related to TG02 should be managed as outlined in the tables below.

Cycles 2+: TG02 dose reductions and skipped dose(s) can be made for adverse events as described in the tables below.

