- Any non-hematological grade III–IV toxicity according to CTCAE, Version 5.0 with the exclusion of alopecia and asymptomatic or reversible laboratory abnormalities which can be rapidly controlled with appropriate measures. This acute toxicity must be declared as possibly related by the clinical investigator in order to be taken into account in the decision rule.
- An absolute neutrophil count $< 0.5 \times 10^9/L$ lasting for ≥ 7 days
- Febrile neutropenia defined as an absolute neutrophil count $< 0.5 \times 10^9/L$ and fever of at least $38.5^\circ C$
- Thrombocytopenia grade III with bleeding or any grade IV according to CTCAE, Version 5.0

- Nausea, vomiting or diarrhea grade III-IV not controlled after 48 h of maximal antiemetic or antidiarrheal treatment
- Any toxicity not qualifying for DLT but which does not allow intake of 75% of intended dose intensity of TG02 or of RT

EXPANSION

After dose escalation is completed, additional patients will be enrolled at MTD up to a total of 24 evaluable patients in Group A. Expansion at the predetermined MTD will be stopped if 2 or more of the first 6 patients, or 33% or more of the patients thereafter, experience a DLT. The expansion cohort will be fully enrolled at the next lower dose level. If there are again 2 DLT in the first 6 patients, expansion will be stopped in that arm.

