Grade 4 event	Skip one or more doses of TG02 until improved to grade ≤ 1 . Consider the individual benefit versus the risk of continuing TG02. If TG02 is re-introduced, re-introduce at a reduced dose*. If TG02 has been re-introduced after a second event and the event recurs, discontinue TG02.
Recurrence of the same grade 4 event	Discontinue TG02.
Neutropenia	
First occurrence of grade 3 event	Skip one or more doses of TG02 until improved to grade ≤ 1 . Re-introduce TG02 at a reduced dose *
Recurrence of the same grade 3 event	Skip one or more doses of TG02 until improved to grade ≤ 1 . Re-introduce TG02 at a reduced dose * If TG02 has been re-introduced after a second event and the event recurs, consider the individual benefit versus the risk of continuing TG02. If TG02 is re-introduced, re-introduce TG02 at a reduced dose *. If TG02 has been re-introduced after a third event and the event recurs, discontinue TG02.
Grade 4 event	Skip one or more doses of TG02 until improved to grade ≤ 1 . Re-introduce TG02 at a reduced dose *.
Recurrence of the same grade 4 event	Discontinue TG02.
Febrile Neutropenia	
Grade 3 or 4 event	Skip one or more doses of TG02 until fever is resolved and neutropenia is improved to grade ≤ 1 . Re-introduce TG02 at a reduced dose *

Adverse Event	Action to be taken with TG02
Recurrence of the same grade 3 event	Skip one or more doses of TG02 until improved to grade ≤ 1 . Consider the individual benefit versus the risk of continuing TG02. If TG02 is re-introduced, re-introduce TG02 at a reduced dose *. If TG02 has been re-introduced after a second event and the event recurs, discontinue TG02.
Recurrence of the same grade 4 event	Discontinue TG02.

Group A: TG02-related Non-hematologic Adverse Events

Adverse Event	Action to be taken with TG02
Nausea/ Vomiting	
Grade 1 or 2 event	Manage with moderate anti-emetic treatment until improved to grade ≤ 1 . Prophylaxis should be given before TG02 dosing (see Section 5.6.2). If a patient experiences persistent or recurrent grade 2 nausea/vomiting that do not improve to grade ≤ 1 with maximal supportive measures within 3 days, then TG02 dosing should be skipped until improved to grade ≤ 1 . The dose of TG02 may be reduced *

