5.5.3.3 Group B

5.5.3.3.1 Dose escalation phase

Cycle 1: no TG02 or TMZ dose reductions are allowed in Cycle 1 except if a patient experiences a DLT.

Skipped doses of TG02 are allowed. A "skipped dose" for TG02 when TMZ is not interrupted means that one or more single doses will be omitted and not replaced, in order not to change the temporal relationship with TMZ.

For example, if TG02 is planned on days 1, 4 and 22, but day 4 has to be omitted, TG02 can be restarted on day 22 if the AE is sufficiently resolved: TG02 is always restarted on a scheduled dose day.

Interruptions of TMZ are allowed.

Skipping TG02 or interrupting TMZ for >25% of the planned total dose in Cycle 1 will be considered a DLT (see section 5.5.1).

Toxicities possibly related to TG02 should be managed as outlined in the tables below. Toxicities of TMZ should be managed as outlined in the table below and per local practice, where noted.

Cycles 2+: TG02 dose reductions and skipped dose(s) can be made for adverse events as described in the tables below. TMZ dose reductions and interruptions can be made for adverse events as described in section 5.5.2 and the tables below.

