8.1 Statistical design

8.1.1 Sample size

Groups A and B

This is an open label, non-randomized, multi-center trial using the classical 3+3 design.

In both groups A and B, a minimum of 3 patients will be included at each dose level. There is no intention to increase the dose of TG02 above 150 mg in Groups A and B. Within one dose level, patients may be entered simultaneously. The second dose level may be started when all patients of dose level 1 have completed cycle 1 (28 days).

In case of occurrence of 1 DLT, an additional 3 patients will be added in order to ensure the safety profile of this dose level unless a DLT is documented immediately in any additional patient entered at this dose level. If 2 DLT are observed in the first 3 patients dose escalation will stop without need to extend the dose level to 6 patients.

The replacement of patients will be performed in case of patients that progress, die due to disease progression, or leave study for any reason other than DLT prior to completion of the first cycle of therapy.

After determination of the MTD, additional patients will be treated at the highest dose level for additional safety information in the absence of safety issues up to a total of 24 evaluable patients in Group A and up to a total of 12 evaluable patients in Group B (up to 36 evaluable patients for Groups A and B). We consider groups A and B exploratory and independent from each other, with the prime goal of assessing feasibility (tolerability, safety). The difference in size in these two groups reflects the natural distribution of patients into those with tumors without (2/3, group A) and with (1/3, group B) MGMT promoter methylation. The elderly patient population is ideally suited to explore safety, tolerability and efficacy of TG02 with the two backbones of glioblastoma treatment, radiotherapy (group A) and temozolomide (group B), in isolation. Finally, there is a feasibility consideration: we anticipate that doctors and patients are more willing to omit temozolomide in group A than to omit radiotherapy in arm B although such a strategy is consistent with the EANO guideline updated in 2017 (Ref. 35).

Number of Patients with DLT at a Dose Level	Dose Escalation Decision Rule in Groups A and B
0 out of 3	Enroll 3 patients at the next dose level up to a maximum TG02 dose of 150 mg.

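### In escalation cycle 1 of Groups A and B, the TG02 rules for a grade 3 neutropenia that is not itself a DLT are not reconciled, and mainly at 100 mg the DLT result can depend on which rule is followed

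*Combined protocol and SAP*

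**What the plan says.** - **Ban on reductions.** Section 5.5.3.2.1, cycle 1 of Group A escalation: "no TG02 dose reductions are allowed in Cycle 1, except if a patient experiences a DLT". Section 5.5.3.3.1, Group B: "no TG02 or TMZ dose reductions are allowed in Cycle 1 except if a patient experiences a DLT". Skipped doses are allowed in both.
- **Referral to the tables.** The same cycle 1 text in 5.5.3.2.1 adds: "Toxicities possibly related to TG02 should be managed as outlined in the tables below". Section 5.5.3.3.1 has a matching sentence.
- **What the tables require.** For a first grade 3 neutropenia, the Group A table (under 5.5.3.2.2) says to skip TG02 until grade 1 or lower and then "Re-introduce TG02 at a reduced dose". The Group B table (5.5.3.3.3) also requires reduced TG02. The grade 4 rows do likewise.
- **The 100 mg floor.** For patients already on 100 mg, section 5.5.3.1 (all groups) provides that when "the patient experiences a toxicity requiring TG02 dose reduction as described in the tables below, the patient should be discontinued from study treatment". Both groups start at 100 mg.
- **DLT definition.** In 5.2.1.1 and 5.2.1.2, neutropenia is a DLT if the count is below 0.5 x 10^9/L for at least 7 days, or is below that level with fever. A separate clause covers any other toxicity that "does not allow intake of 75% of intended dose intensity of TG02 or of RT" (for Group B, TG02 or TMZ). Sections 5.5.3.2.1 and 5.5.3.3.1 also make skipping more than 25% of planned cycle 1 TG02 a DLT.
- **Use of the result.** At most 1 DLT in 6 is acceptable (8.1.1). Two or more at 100 mg closes the arm; two or more at 150 mg sets the MTD at 100 mg.

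**The concern.** A first grade 3 neutropenia, or a brief grade 4 without fever, meets neither neutrophil criterion. The exception in the ban therefore does not apply, and the patient should not be reduced. The tables nevertheless require a reduction, and at 100 mg section 5.5.3.1 converts it into stopping treatment. A ban on reductions does not by its terms cancel an order to discontinue. Two sites with the same patient could act differently, and because stopping or reducing lowers intake, they could also report different DLT outcomes.

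The MTD is the primary endpoint of Groups A and B (2.2.1) and rests on three to six patients per level. The event is foreseeable: section 1.3.3.2 names grade 3 or 4 neutropenia among the findings that preceded the IDMC's dose recommendations.

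**Working it through.** The plan states no figure to reproduce here. The check is to count cycle 1 TG02 intake under each instruction and compare it with 75%.

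**Inputs.** Group A plans six cycle 1 doses, on Days 1, 4, 8, 11, 15 and 18 (5.2.1.1). Group B plans six, on Days -7, -4, 1, 4, 22 and 25 (5.2.1.2). Planned totals are 600 mg at 100 mg and 900 mg at 150 mg. After Day 1, scheduled cycle 1 counts are on Days 8 and 15 in Group A (6.2.1.2) and on Days 8, 15 and 22 in Group B (6.2.2.2).

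**Formula.** Intake = mg taken / mg planned. *Resume* means the same dose after recovery. *Table* means 100 mg after recovery if the patient was on 150 mg, and discontinuation under 5.5.3.1 if on 100 mg.

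| Path | Resume | Table | DLT result |
|---|---|---|---|
| B, 100 mg, found Day 8 or 15, recovered by Day 22 | 6/6 = 100% | 4/6 = 67% | changes |
| A, 100 mg, found Day 8, one skip | 5/6 = 83% | 2/6 = 33% | changes |
| A, 100 mg, found Day 15, one skip | 5/6 = 83% | 4/6 = 67% | changes |
| A, 150 mg, found Day 8, one skip | 750/900 = 83% | (2x150 + 3x100)/900 = 67% | changes |
| A, 150 mg, found Day 15, one skip | 750/900 = 83% | (4x150 + 100)/900 = 78% | no DLT either way |
| B, 150 mg, found Day 8, 15 or 22, one skip | 750/900 = 83% | 700/900 = 78% | no DLT either way |
| Any group or dose, two or more skips | at most 4/6 = 67% | at most 67% | DLT either way |

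**Which paths arise on scheduled counts.** In Group A, an event found on Day 8 is next checked on Day 15, so Days 8 and 11 are lost: 4/6 = 67%. An event found on Day 15 loses Days 15 and 18: again 67%. Both are DLTs under either instruction. The Group A rows that change therefore need an extra count and recovery to grade 1 or lower within about three days. The Group B 100 mg row needs no extra count, because no TG02 is due between Days 4 and 22.

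**Two tests that disagree.** In the Group A 150 mg Day 8 path under the table, 1 of 6 doses is skipped (17%), which is not a DLT by the skipped-dose test. Intake is 67%, which is a DLT by the dose-intensity clause. The path is also circular: reduction is barred without a DLT, yet the reduction produces one.

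**Effect on 3+3.** One reclassified patient turns 0/3 into 1/3 (three more patients) or 1/6 into 2/6 (the level fails). With DLT probability p and q = 1 - p, P(level passes) = q^3 + 3pq^5.

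The event rate at 100-150 mg is not given, so suppose that 10%, 20% or 30% of patients have such an event and that all convert to DLTs at 100 mg:

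- No other DLTs: P(arm closes) = 9%, 29%, 51%, against 0% if none convert.
- Assumed 10% background DLT risk, so p = 1 - 0.9(1 - rate) = 0.19, 0.28, 0.37: 27%, 46%, 64%, against 9%.

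These are upper bounds. They assume that every event converts under one reading and that none is a DLT under the other.

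**The case against.** The best defence is that the text can be read coherently. After the cycle 1 ban, 5.5.3.2.1 says that from cycle 2 reductions may follow the tables, and 5.5.3.2.2 contrasts this by allowing them in any cycle during expansion. Sections 5.5.3.3.1 and 5.5.3.3.2 follow much the same pattern. Reading the specific over the general, in escalation cycle 1 the tables would govern only skipping and recovery grade. No reduction would then be required, and 5.5.3.1 would not be triggered. Sites are also told to contact the sponsor when unsure (5.5.3.1), and each cohort is reviewed before escalation (18.1).

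This is a plausible account of the intent, and it weakens any claim that sites will routinely diverge. It does not close the gap. The referral to the tables sits inside the cycle 1 text, and nothing says that the ban overrides the tables or suspends 5.5.3.1. Case-by-case advice and cohort review are not a scoring rule.

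Four stronger readings are tempting and are not supported:

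- *Every such neutropenia changes the DLT result.* It does not; see the unchanged paths above.
- *The rate is about 41%.* The 5 of 12 in 5.2.1.2 comes from TG02 200 or 250 mg with a different TMZ schedule. It is not stated to be cycle 1, nor to exclude events that are DLTs anyway.
- *One reclassified patient closes an arm.* Closure needs another DLT as well.
- *A patient stopped at 100 mg may be replaced.* Section 8.1.1 replaces patients who "leave study for any reason other than DLT prior to completion of the first cycle of therapy". In these paths the 75% clause already makes the patient a DLT, so replacement would be miscoding.

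**Conclusion.** The concern holds in a limited form. The cycle 1 ban, the tables and the 100 mg rule are not reconciled for a neutropenia that is not itself a DLT, and the outcome feeds the primary endpoint. The exposure is mainly at 100 mg. The clear case on scheduled counts is Group B at 100 mg (100% against 67%). It rests on recovery to grade 1 or lower by Day 22 and, for a Day 15 event, on the Day 22 count in 6.2.2.2; footnote 7 of the Group B summary table (6.4.2) lists only Days 8 and 15 among the mid-cycle counts.

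Group A is affected only with an unscheduled count and a single skipped dose. At 150 mg the exposure is narrow. A Group B event on Day 1 could also change by TG02 arithmetic, but would probably be a DLT through the TMZ interruption rule (5.5.2).

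How often this will occur cannot be estimated from the documents. The closure probabilities above show sensitivity under assumed rates and are not forecasts.

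**What to change.** 1. Reconcile 5.5.3.1, 5.5.3.2.1, 5.5.3.3.1 and the neutropenia rows of both tables with the DLT definitions in 5.2.1.1 and 5.2.1.2, so that one stated instruction applies in escalation cycle 1. Which clinical rule that is remains for the sponsor and the IDMC.
2. Check every other row that requires a reduction for an event that may not be a DLT. One example is Group B first grade 3 hepatotoxicity, since 5.2.1.2 excludes asymptomatic or reversible laboratory abnormalities that are rapidly controlled.
3. Align the skipped-dose test with the dose-intensity test, so that one patient cannot pass one and fail the other.
4. In 5.2.1 and 8.1.1, give one DLT and replacement classification for a patient reduced or stopped in cycle 1 for TG02-related toxicity.

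The cost is protocol wording and a letter to sites, with no added patients or tests. Some patients may be scored differently from how they would be now.

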5.5.3.2.2 Expansion phase

TG02 dose reductions and skipped dose(s) are allowed in any cycle. A “skipped dose” for TG02 means that one or more single doses will be omitted and not replaced, in order not to change the temporal relationship.

For example, if TG02 is planned on days 1, 4, 8 but day 4 has to be omitted, TG02 can be restarted on day 8 if the AE is sufficiently resolved: TG02 is always restarted on a scheduled dose day.

Toxicities possibly related to TG02 should be managed as outlined in the tables below.

NOTE: * in below tables: There will be no dose reductions below 100 mg TG02 BIW

Group A: TG02-related Hematological Adverse Events

Adverse Event	Action to be taken with TG02
Thrombocytopenia	
First occurrence of grade 3 without bleeding	Skip one or more doses of TG02 until improved to grade ≤ 1 . Re-introduce TG02 at initial dose.
Recurrence of the same grade 3 event without bleeding	Skip one or more doses of TG02 until improved to grade ≤ 1 . Re-introduce TG02 at a reduced dose* If TG02 has been re-introduced after a second event and the event recurs, consider the individual benefit versus the risk of continuing TG02. If TG02 is re-introduced, re-introduce at a reduced dose * If TG02 has been re-introduced after a third event and the event recurs, discontinue TG02.
First occurrence of grade 3 with bleeding or grade 4 event	Skip one or more doses of TG02 until improved to grade ≤ 1 . Re-introduce TG02 at a reduced dose *
Recurrence of the same grade 3 event with bleeding	Skip one or more doses of TG02 until improved to grade ≤ 1 . Consider the individual benefit versus the risk of continuing TG02. If TG02 is re-introduced, re-introduce at a reduced dose * If TG02 has been re-introduced after a second event and the event recurs, discontinue TG02.

Adverse Event	Action to be taken with TG02
Recurrence of the same grade 4 event	Discontinue TG02.
Anemia	
First occurrence of grade 3 event	Skip one or more doses of TG02 until improved to grade ≤ 2 . Re-introduce TG02 at initial dose.
Recurrence of the same grade 3 event	Skip one or more doses of TG02 until improved to grade ≤ 2 . Re-introduce TG02 at a reduced dose*. If TG02 has been re-introduced after a second event and the event recurs, discontinue TG02.
Grade 4 event	Skip one or more doses of TG02 until improved to grade ≤ 1 . Consider the individual benefit versus the risk of continuing TG02. If TG02 is re-introduced, re-introduce at a reduced dose*. If TG02 has been re-introduced after a second event and the event recurs, discontinue TG02.
Recurrence of the same grade 4 event	Discontinue TG02.
Neutropenia	
First occurrence of grade 3 event	Skip one or more doses of TG02 until improved to grade ≤ 1 . Re-introduce TG02 at a reduced dose *
Recurrence of the same grade 3 event	Skip one or more doses of TG02 until improved to grade ≤ 1 . Re-introduce TG02 at a reduced dose * If TG02 has been re-introduced after a second event and the event recurs, consider the individual benefit versus the risk of continuing TG02. If TG02 is re-introduced, re-introduce TG02 at a reduced dose *. If TG02 has been re-introduced after a third event and the event recurs, discontinue TG02.
Grade 4 event	Skip one or more doses of TG02 until improved to grade ≤ 1 . Re-introduce TG02 at a reduced dose *.
Recurrence of the same grade 4 event	Discontinue TG02.
Febrile Neutropenia	
Grade 3 or 4 event	Skip one or more doses of TG02 until fever is resolved and neutropenia is improved to grade ≤ 1 . Re-introduce TG02 at a reduced dose *

Adverse Event	Action to be taken with TG02
Recurrence of the same grade 3 event	Skip one or more doses of TG02 until improved to grade ≤ 1 . Consider the individual benefit versus the risk of continuing TG02. If TG02 is re-introduced, re-introduce TG02 at a reduced dose *. If TG02 has been re-introduced after a second event and the event recurs, discontinue TG02.
Recurrence of the same grade 4 event	Discontinue TG02.

Group A: TG02-related Non-hematologic Adverse Events

Adverse Event	Action to be taken with TG02
Nausea/ Vomiting	
Grade 1 or 2 event	Manage with moderate anti-emetic treatment until improved to grade ≤ 1 . Prophylaxis should be given before TG02 dosing (see Section 5.6.2). If a patient experiences persistent or recurrent grade 2 nausea/vomiting that do not improve to grade ≤ 1 with maximal supportive measures within 3 days, then TG02 dosing should be skipped until improved to grade ≤ 1 . The dose of TG02 may be reduced *
Grade 3 nausea Grade 3 or 4 vomiting	Skip one or more doses of TG02 until improved to grade ≤ 1 . If improved to grade ≤ 1 in <48 hours, re-introduce TG02 at the initial dose. If not improved to grade ≤ 1 with maximal supportive measures within 48 hours, re-introduce TG02 at a reduced dose *. Continue prophylaxis and management with at least moderate anti-emetic treatment (see Section 5.6.2).
Diarrhea	
Grade 1 or 2 event	Manage with anti-diarrheal treatment until improved to grade ≤ 1 . Prophylaxis should be given before TG02 dosing (see Section 5.6.2). If a patient experiences persistent or recurrent grade 2 diarrhea that does not improve to grade ≤ 1 with maximal supportive measures within 3 days, then TG02 dosing should be skipped until improved to grade ≤ 1 . The dose of TG02 may be reduced *. Continue prophylaxis and management with anti-diarrheal treatment (see Section 5.6.2).

Adverse Event	Action to be taken with TG02
Grade 3 or 4 event	
Skip one or more doses of TG02 until improved to grade ≤ 1. Physician should instruct patient regarding hydration. If improved to grade ≤ 1 in <48 hours, re-introduce TG02 at the initial dose.
 
If not improved to grade ≤ 1 with maximal supportive measures within 48 hours, re-introduce TG02 at a reduced dose *.
 
Continue prophylaxis and management with anti-diarrheal treatment (see Section 5.6.2)

Other non-hematologic events except alopecia and asymptomatic or reversible laboratory abnormalities	
First occurrence of grade 3 event	Skip one or more doses of TG02 until improved to grade ≤ 1 . Provide appropriate symptomatic treatment. Re-introduce TG02 at initial dose.
Second occurrence of the same grade 3 event	
Skip one or more doses of TG02 until improved to grade ≤ 1. Provide appropriate symptomatic treatment. Re-introduce TG02 at a reduced dose *.
 
If TG02 has been re-introduced after a second event and the event recurs, consider the individual benefit versus the risk of continuing TG02. If TG02 is re-introduced, re-introduce TG02 at a reduced dose *.
 
If TG02 has been re-introduced after a third event and the event recurs, discontinue TG02.

First occurrence of the same grade 4 event	Skip one or more doses of TG02 until improved to grade ≤ 1 . Provide appropriate symptomatic treatment. Re-introduce TG02 at a reduced dose*.
Second occurrence of the same grade 4 event	
Skip one or more doses of TG02 until improved to grade ≤ 1. Provide appropriate symptomatic treatment. Consider the individual benefit versus the risk of continuing TG02. If TG02 is re-introduced, re-introduce TG02 at a reduced dose*.
 
If TG02 has been re-introduced after a second event and the event recurs, discontinue TG02.

